PTT	Partial Thromboplastin Time
SAE	Serious Adverse Event
SAP	Statistical Analysis Plan
SICT	Satisfaction with Iron Chelation Therapy
SD	Standard Deviation
SOC	System Organ Class
SUSAR	Serious unexpected suspected adverse reactions
TDT	Transfusion-dependent thalassemia

Abbreviation/Term	Definition
UGT	Uridine diphosphate glucuronosyltransferase
ULN	Upper Limit of Normal
WOCBP	Woman of childbearing potential

1. INTRODUCTION

1.1 Background

Commercial deferasirox (DFX) is an orally active chelator that is selective for iron (as Fe^{3+}). It is a tridentate ligand that binds iron with high affinity in a 2:1 ratio. Although DFX has very low affinity for zinc and copper there are variable decreases in the serum concentration of these trace metals after the administration of DFX. The clinical significance of these decreases is uncertain [1].

DFX is indicated for the treatment of chronic iron overload due to blood transfusions in patients 2 years of age and older; and for the treatment of chronic iron overload in patients 10 years of age and older with non-transfusion-dependent thalassemia syndromes and with a liver iron concentration of at least 5 mg of iron per gram of dry weight (Fe/g dw) and a serum ferritin greater than 300 mcg/L [1].

DFX is formulated as a tablet for suspension as Exjade[®]. The package insert ([Appendix A](#); Novartis, Exjade) recommends that Exjade be dispersed in water or fruit juice [1]. Additionally, DFX is also available as an oral film coated tablet or granules ([Appendix B](#); Novartis, Jadenu[®]) [2] that presents improved bioavailability versus Exjade without the need to disperse prior to administration.

The goal of DisperSol Technologies, LLC (“DisperSol”) is to develop a patient friendly formulation of deferasirox, DST-0509 (Deferasirox) Tablets, which will be more consistently bioavailable than existing marketed products, and more bioavailable in situations where poor bioavailability has compromised the iron binding capability of the drug. It therefore offers the potential to be a therapeutic option in the difficult to treat arena of iron overload and may help treat refractory iron overloaded patients who are not responding to current therapies.

DST-0509 is manufactured using a thermokinetic mixing process, or fusion process to produce drug-polymer composites, and specifically an amorphous drug-polymer intermediate. The process has been repeatedly demonstrated in the pharmaceutical literature to produce amorphous drug-polymer intermediates with compounds that could not be successfully melt-extruded owing to their high melting points. The composition provides improved DFX solubility and dissolution properties that may result in enhanced bioavailability and reduced pharmacokinetic variability in patients. These attributes are expected to translate into less variability in response, and improved efficacy in non-responders as compared to existing marketed DFX products.

The FDA approved initial dose of Exjade is 20 mg/kg and may be titrated up to 40 mg/kg [1]. The dosing of Jadenu is initially 7 or 14 mg per kg body weight (depending on the indication) orally, once daily [2]. The maximum recommended dosage of Jadenu is 28 mg per kg body weight orally, once daily [2]. Galanello, et al reported that ICL670 (Exjade) was well tolerated, and no safety problems occurred up to 80 mg/kg following administration of a single dose [4].

DFX is absorbed following oral administration with median times to maximum plasma concentration (T_{max}) of about 1.5 to 4 hours. The C_{max} and AUC of DFX increase approximately linearly after both single administration and under steady-state conditions. Exposure to DFX increased by an accumulation factor of 1.3-2.3 after multiple doses. The absolute bioavailability (AUC) of DFX tablets for oral suspension is 70% compared to an intravenous dose. The bioavailability (AUC) of DFX was variably increased when taken with a meal [1,2].

DFX is highly (~99%) protein bound almost exclusively to serum albumin. The percentage of DFX confined to the blood cells was 5% in humans. The volume of distribution at steady-state of DFX is 14.37 ± 2.69 L in adults. Glucuronidation is the main metabolic pathway for DFX, with subsequent biliary excretion.

DFX and metabolites are primarily (84% of the dose) excreted in the feces. Renal excretion of DFX and metabolites is minimal (8% of the administered dose). The mean elimination half-life ($t_{1/2}$) ranged from 8-16 hours following oral administration [1,2]

1.2 Clinical Studies

In patients with transfusional iron overload, the most frequently occurring (>5%) adverse reactions are diarrhea, vomiting, nausea, abdominal pain, skin rashes, and increases in serum creatinine. In DFX-treated patients with non-transfusion-dependent thalassemia syndromes, the most frequently occurring (>5%) adverse reactions are diarrhea, rash and nausea [1,2].

Overall, in patients treated with Exjade and Jadenu, gallstones and related biliary disorders were reported in about 2% of patients. Elevations of liver transaminases were reported as an adverse reaction in 2% of patients. Elevations of transaminases greater than 10 times the upper limit of the normal range, suggestive of hepatitis, were uncommon (0.3%). During post-marketing experience, hepatic failure, sometimes fatal, has been reported with the DFX dispersible tablet formulation, especially in patients with pre-existing liver cirrhosis. There have been post-marketing reports of metabolic acidosis [3]. The majority of these patients had renal impairment, renal tubulopathy (Fanconi syndrome) or diarrhea, or conditions where acid-base imbalance is a known complication. Cases of serious acute pancreatitis were observed without

documented underlying biliary conditions. As with other iron chelator treatment, high-frequency hearing loss and lenticular opacities (early cataracts) have been uncommonly observed in patients treated with DFX. In a retrospective meta-analysis of 2,102 adult and pediatric beta-thalassemia patients with transfusional iron overload treated with DFX dispersible tablets (two randomized and four open-label studies of up to five years' duration), a mean creatinine clearance decrease of 13.2% in adult patients (95% CI: -14.4% to -12.1%; n=935), and 9.9% (95% CI: -11.1% to -8.6%; n=1,142) in pediatric patients, was observed during the first year of treatment. In 250 patients who were followed for up to five years, no further decrease in mean creatinine clearance levels was observed [1,2,5].

A food effect study involving administration of DFX as Jadenu to healthy subjects under fasting conditions and with a low-fat (fat content <7% of total calories) or high-fat (fat content >50% of total calories) meal indicated that the AUC and C_{max} were slightly decreased after a low-fat meal (by 11% and 16%, respectively). After a high-fat meal, AUC and C_{max} were increased by 18% and 29%, respectively. The increases in C_{max} due to the change in formulation and due to the effect of a high-fat meal may be additive and therefore, it is recommended that DFX as Jadenu should be taken on an empty stomach or with a light meal (contains less than 7% fat content and approximately 250 calories) [5].

To date, two Phase 1 studies with DST-0509 have been performed. A non-US Phase 1 pilot PK study (OPA-P8-807; Study 101) has been completed in Canada. The study was titled, "Single Dose Crossover Comparative Oral Bioavailability Under Fasting Conditions and Food Effect Pilot Study of Two Deferasirox Formulations and Jadenu 360 mg Tablets in Healthy Male and Female Volunteers". This Phase 1 study was a first-in-human, single center, single dose, crossover oral bioavailability pilot study. The purpose of the Phase 1 study was to provide PK data for two oral dose formulations of DST-0509 following oral administration to healthy subjects in fed and fasted states, compared with Jadenu. The results showed that as hypothesized, the Test (DST-0509) and Reference (Jadenu) formulations were not bioequivalent, with higher bioavailability on a molar basis for the DST-0509 test formulations.

The second Phase 1 study (DIS-P4-592; Study 102) has been completed in Canada. The study was titled "Single Dose Crossover Oral Bioavailability Study of a New Deferasirox Formulation Compared to Exjade Dispersible Tablets and Jadenu Tablets in Healthy Male and Female Volunteers." This was a single center, single dose, randomized, 3-period, 3-sequence crossover, oral bioavailability study of DST-0509 compared with Exjade and Jadenu in fasted healthy volunteers. The results showed less variability in C_{max} and AUC with DST-0509 versus Exjade,

and meaningfully enhanced absorption of DST-0509 versus Exjade and Jadenu. The enhanced bioavailability and reduced PK variability observed in Study 102 on an equivalent molar basis are expected to translate into less variability in response and improved efficacy in patients who do not respond well to currently available DFX products.

This current pilot study is a multicenter, open-label, two-period crossover design that evaluates the safety, tolerability, pharmacokinetics and preliminary evidence of iron chelating activity of DST-0509 as compared to Jadenu and Exjade in transfusion-dependent thalassemia patients with transfusional iron overload, requiring iron chelation therapy and demonstrating an inadequate response to Jadenu or Exjade for greater than 3 months duration. Up to 36 patients will be evaluated (18 in each treatment arm), however, the balanced randomization may enroll fewer patients based on recruitment status.

Rationale for the study design is detailed in [Section 3.2](#).

2 OBJECTIVES

2.1 Primary

This patient-pilot study will assess the safety, overall tolerability, and preliminary evidence of DST-0509 iron chelating activity compared to Jadenu or Exjade in patients with transfusion-dependent beta thalassemia (TDT), major or intermedia, or non-TDT patients with inadequate response to available deferasirox chelation therapy, defined as a liver iron (Fe) concentration (LIC) of at least 5 mg Fe/g dw and a serum ferritin greater than 800 mcg/L.

2.2 Secondary

To determine the single and multiple dose pharmacokinetic (PK) profile of total deferasirox (iron-bound and unbound) plasma concentrations during DST-0509 and Jadenu or Exjade treatments in fed TDT and NTDT patients.

3 INVESTIGATIONAL PLAN

[figure not shown]
3.1 Overall Study Design

This is a multi-center, open-label, two-period cross-over, patient-pilot study comparing DST-0509 to Exjade or Jadenu administered orally once daily (QD) for 28-days in each period, with a 7-day washout before study entry and between treatment periods (see Table 6-1). Patients will be randomized to one of two treatment sequences: DST-0509→Exjade/Jadenu or Exjade/Jadenu→DST-0509 (with subjects who were taking Exjade prior to study start receiving Exjade and those taking Jadenu at study start receiving Jadenu). This study is designed to assess the safety, tolerability, evidence of iron chelating activity, and PK profile of DST-0509 compared to Jadenu or Exjade in inadequately responding patients. Inadequate response to standard chelation therapy is defined from the medical literature [6,7].

Up to 36 patients will be randomized 1:1 into one of two treatment sequences (study arms), of which up to 100% may be on Jadenu or Exjade at study entry, or a mix of the two. The planned randomization will assign up to 18 patients in each of two sequences: Sequence A: DST-0509 crossed to Exjade or Jadenu; Sequence B: Jadenu or Exjade crossed to DST-0509. The comparator treatment will be the patient's current chelation treatment. At the end of the study, patients previously on Jadenu or Exjade will revert to receiving their pre-study medication and dose following a 7-day washout period. A sufficient number of patients will be enrolled so there will be no need to replace study drop-outs. Study duration is approximately 14 weeks for each patient. A Study Flow Diagram is presented after this Synopsis (see Figure 3-1).

Figure 3-1: Study Flow Diagram

Treatment A (28 days) = DST-0509
Treatment B (28 days) = Jadenu/Exjade¹

*Up to 36 patients are planned.

- Subjects taking Exjade prior to study start will receive Exjade (treatment B) in the assigned Period 1 or cross-over Period 2. Those patients taking Jadenu prior to study start will receive Jadenu (treatment B) in the assigned Period 1 or cross-over Period 2. Dosing will be at equivalent (mg for mg) doses of DST-0509 for Jadenu. If crossing over from Exjade to DST-0509, or vice versa, the dose will be scaled to 28 mg/40 mg (DST-0509/Exjade).
- For all patients entering the trial, a 7-day washout is required.
- Visit 11 will be a phone call from study staff to the patient. The phone call will confirm that the patient has conducted the 7-day washout period before recommencing prior iron chelation therapy. AEs and concomitant medications will also be collected by phone on Visit 11.

3.2 Discussion of Study Design

This multi-dose 2-period, 2-arm crossover design was selected to adequately evaluate and compare the safety, tolerability and efficacy of DST-0509 compared to Jadenu and Exjade.

A 7-day washout period will be employed before the first treatment period, in between study treatments and at the end of the study, in order to clear the patient's system of any previous iron chelation treatment.

The choice of the drug strength used was justified based on analytical, pharmacokinetic and safety grounds. Furthermore, this strength was the Reference Listed Drug recommended by the FDA as follows. The FDA approved initial dose of DFX is 20 mg/kg and may be titrated up to 40 mg/kg with the Exjade formulation [1]. The dosing of Jadenu is initially 7 or 14 mg per kg body weight (depending on the indication) orally, once daily [2]. The maximum recommended dosage of DFX as Jadenu is 28 mg per kg body weight orally, once daily [2].

A food effect study involving administration of DFX as Jadenu to healthy subjects under fasting conditions and with a low-fat (fat content <7% of total calories) or high-fat (fat content >50% of total calories) meal indicated that the AUC and C_{max} were slightly decreased after a low-fat meal (by 11% and 16%, respectively). After a high-fat meal, AUC and C_{max} were increased by 18% and 29%, respectively. The increases in C_{max} due to the change in formulation and due to the effect of a high-fat meal may be additive and therefore, it is recommended that DFX as Jadenu should be taken on an empty stomach or with a light meal (contains less than 7% fat content and approximately 250 calories) [2].

Because DFX is rated in the pregnancy category C1, women will be included in the present study, provided they consent to take appropriate measures to prevent pregnancy for at least 28 days prior to the first administration of the study drug, during the study and for at least 30 days after the last dose of the study drug. Additionally, if the participant is using systemic contraceptives, she must use an additional non-hormonal form of acceptable method of contraception during the study and for at least 30 days after the last dose of the study drug.

4 SELECTION AND WITHDRAWAL OF PATIENTS

The study will enroll up to 36 patients and no study drop-outs will be replaced. Patients who have provided written informed consent and an authorization for disclosure of protected health information must meet all of the following criteria to qualify for entry into the study.

4.1 Inclusion Criteria

1. Written informed consent obtained prior to any study-related procedure being performed;
2. Patients at least 18 years of age or older at the time of consent;
3. Patient with TDT or NTDT syndromes and iron overload currently receiving iron chelation therapy with Jadenu or Exjade and demonstrating inadequate response assessed with serum ferritin and LIC;
4. Stable dosing with Jadenu or Exjade for >3 months prior to screening and receiving the maximal dose (Jadenu: 28 mg/kg or Exjade: 40 mg/kg);
5. Serum ferritin levels that are persistently >800 mcg/L determined by 2 separate assessments during screening over the previous 2-4 weeks prior to study treatment and not showing a decreasing trend over these weeks;
6. An LIC of >5 mg Fe/g dw measured by MRI in the 52 weeks prior to study entry;
7. Compliant with chelation therapy in the 3 months prior to enrollment as assessed by the Investigator:
 - a. Satisfaction with Iron Chelation Therapy (SICT) Quality of Life (QoL) composite score $\geq 60\%$, or determined by investigator that at least 75% of medication prescribed on a regular basis was taken (Investigator enquiry into patient prescription refill records, preferably 3 months if available); and
 - b. Willing to comply with chelation therapy for the duration of the study;
8. Agree not to use other anti-chelating agents concurrently;
9. Eastern Cooperative Oncology Group Performance Status (ECOG PS) of 0-1;
10. Women of childbearing potential (WOCBP) must use an adequate method of birth control (double barrier, e.g. hormonal control and barrier contraception) at least 28

days prior to the first administration of the study drug, during the study and for at least 30 days after the last dose of the study drug. (Section 7.5 for details);

11. Male patients whose partners are WOCBP must use an adequate method of birth control (double barrier control) at least 28 days prior to the first administration of the study drug, during the study and for at least 30 days after the last dose of the study drug; and
12. Patient is willing and able to comply with all protocol required visits and assessments.

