
PROPOSED INDICATIONS:
 
 • Treatment of chronic iron overload due to blood transfusions in patients 2 years of age and older when current chronic oral chelation therapy with other deferasirox products is inadequate. • Treatment of chronic iron overload in patients 10 years of age and older with non-transfusion-dependent thalassemia (NTDT) syndromes when current chronic oral chelation therapy with other deferasirox products is inadequate. 
PROPOSED RATIONALE: The efficacy of DST-0509 (deferasirox) tablets will be demonstrated in patients who were inadequately controlled on high doses of Jadenu® (“Jadenu”) or Exjade® (“Exjade”). Patients are defined as inadequate responders if their liver iron (Fe) concentration (LIC) is at least 5 mg Fe per gram of dry weight (Fe/g dw) and serum ferritin is >800 mcg/L, despite compliance with chronic chelation treatment.
	

OBJECTIVES:
 
Primary objectives:
 
 • This patient-pilot study will assess the safety, overall tolerability, and preliminary evidence DST-0509 tablets iron chelating activity compared to Jadenu or Exjade in patients with transfusion-dependent beta thalassemia (TDT), major or intermedia, or non-TDT (NTDT) patients with inadequate response to available deferasirox chelation therapy, defined as an LIC of at least 5 mg Fe/g dw and a serum ferritin >800 mcg/L. 
Secondary objectives:
 
 • To determine the single and multiple dose pharmacokinetic (PK) profile of total deferasirox (iron-bound and unbound) plasma concentrations during DST-0509 and Jadenu or Exjade treatments in fed TDT and NTDT patients. 	

POPULATION:
 
Adult patients (≥18 years) with TDT or NTDT and iron overload currently receiving iron chelation therapy (ICT) with Jadenu or Exjade and demonstrating inadequate response. Inadequate response is defined as serum ferritin levels that are persistently >800 mcg/L, determined by 2 separate assessments over the previous 2-4 weeks and not showing a decreasing trend over these weeks.
 
Patients should also have an LIC of >5 mg Fe/g dw measured by magnetic resonance imaging (MRI) in the 52 weeks prior to study entry and are receiving the maximal dose of oral commercial deferasirox (DFX), Jadenu: 28 mg/kg or Exjade: 40 mg/kg. Patients should be medication compliant in the opinion of the Investigator and willing to comply with treatment in the study.
	

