5.4 Administration of Investigational Product

DST-0509 will be supplied in 360 mg, 180 mg and 90 mg tablets. Jadenu is commercially available as tablets and Exjade as tablets for oral suspension and will be provided by the patient with their ongoing prescription. Dosing will be at equivalent (mg for mg) doses of DST-0509 or Jadenu. If converting from Exjade, the dose will be scaled for each treatment by 28 mg/40 mg (treatment/Exjade).

This is an open-label crossover study. Patients will receive Exjade or Jadenu at their previous stable dose. DST-0509 is taken with food, Jadenu is taken with or without a light meal, and Exjade is recommended to be taken without food. However, either Jadenu or Exjade can be administered according to the patient's previous regimen.

Each subject will be provided with sufficient DST-0509 for the respective treatment period and site staff will ensure prescription for Jaden and Exjade are sufficient for the respective treatment periods. The first dose will be taken at Visit 3 (Day 1) and the final dose will be taken at Visit 10 (Day 63).

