2.2 Iron Overload in Non-Transfusion-Dependent Thalassemia Syndromes

Exjade therapy should only be considered when a patient with NTDT syndrome has an LIC of at least 5 mg Fe/g dw and a serum ferritin greater than 300 mcg/L.

Prior to starting therapy, obtain:

- LIC by liver biopsy or by an FDA-cleared or approved method for identifying patients for treatment with deferasirox therapy
- Serum ferritin level on at least 2 measurements 1 month apart [see *Clinical Studies (14)*]
- Baseline serum creatinine in duplicate (due to variations in measurements) and determine the creatinine clearance (Cockcroft-Gault method) [see *Dosage and Administration (2.4), Warnings and Precautions (5.1)*]
- Serum transaminases and bilirubin [see *Dosage and Administration (2.4), Warnings and Precautions (5.2)*]
- Baseline auditory and ophthalmic examinations [see *Warnings and Precautions (5.9)*]

Initiating therapy:

- The recommended initial dose of Exjade is 10 mg per kg body weight orally once daily. Calculate doses (mg per kg per day) to the nearest whole tablet.
- If the baseline LIC is greater than 15 mg Fe/g dw, consider increasing the dose to 20 mg/kg/day after 4 weeks.

During therapy:

- Monitor serum ferritin monthly. Interrupt treatment when serum ferritin is less than 300 mcg/L and obtain an LIC to determine whether the LIC has fallen to less than 3 mg Fe/g dw.
- Monitor LIC every 6 months.
- After 6 months of therapy, if the LIC remains greater than 7 mg Fe/g dw, increase the dose of deferasirox to a maximum of 20 mg/kg/day. Do not exceed a maximum of 20 mg/kg/day.
- If after 6 months of therapy, the LIC is 3–7 mg Fe/g dw, continue treatment with deferasirox at no more than 10 mg/kg/day.

- When the LIC is less than 3 mg Fe/g dw, interrupt treatment with deferasirox and continue to monitor the LIC.
- Monitor blood counts, hepatic function, and renal function [see *Warnings and Precautions (5.1, 5.2, 5.4)*].

Restart treatment when the LIC rises again to more than 5 mg Fe/g dw.

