2 DOSAGE AND ADMINISTRATION

2.1 Transfusional Iron Overload

JADENU therapy should only be considered when a patient has evidence of chronic transfusional iron overload. The evidence should include the transfusion of at least 100 mL/kg of packed red blood cells (e.g., at least 20 units of packed red blood cells for a 40 kg person or more in individuals weighing more than 40 kg), and a serum ferritin consistently greater than 1000 mcg/L.

Prior to starting therapy, obtain:

- serum ferritin level
- baseline serum creatinine in duplicate (due to variations in measurements) and determine the CrCl_{Cr} (Cockcroft-Gault method) [see *Dosage and Administration (2.4)*, *Warnings and Precautions (5.1)*]
- serum transaminases and bilirubin [see *Dosage and Administration (2.4)*, *Warnings and Precautions (5.2)*]
- baseline auditory and ophthalmic examinations [see *Warnings and Precautions (5.8)*]

The recommended initial dose of JADENU for patients 2 years of age and older is 14 mg per kg body weight orally, once daily. Calculate doses (mg per kg per day) to the nearest whole tablet. Changes in weight of pediatric patients over time must be taken into account when calculating the dose.

After commencing therapy, monitor serum ferritin monthly and adjust the dose of JADENU, if necessary, every 3 to 6 months based on serum ferritin trends. Make dose adjustments in steps of 3.5 or 7 mg per kg and tailor adjustments to the individual patient's response and therapeutic goals. In patients not adequately controlled with doses of 21 mg per kg (e.g., serum ferritin levels persistently above 2500 mcg/L and not showing a decreasing trend over time), doses of up to 28 mg per kg may be considered. Doses above 28 mg per kg are not recommended.

If the serum ferritin falls consistently below 500 mcg/L, consider temporarily interrupting therapy with JADENU [see *Warnings and Precautions (5.9)*].

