2.2 Iron Overload in Non-Transfusion-Dependent Thalassemia Syndromes

JADENU therapy should only be considered when a patient with NTDT syndrome has an LIC of at least 5 mg Fe/g dw and a serum ferritin greater than 300 mcg/L.

Prior to starting therapy, obtain:

- LIC by liver biopsy or by an FDA-cleared or approved method for identifying patients for treatment with deferasirox therapy
- Serum ferritin level on at least 2 measurements 1 month apart [see *Clinical Studies (14)*]
- Baseline serum creatinine in duplicate (due to variations in measurements) and determine the CrCl_{Cr} (Cockcroft-Gault method) [see *Dosage and Administration (2.4)*, *Warnings and Precautions (5.1)*]
- Serum transaminases and bilirubin [see *Dosage and Administration (2.4)*, *Warnings and Precautions (5.2)*]
- Baseline auditory and ophthalmic examinations [see *Warnings and Precautions (5.8)*]

Initiating therapy:

- The recommended initial dose of JADENU is 7 mg per kg body weight orally once daily. Calculate doses (mg per kg per day) to the nearest whole tablet.
- If the baseline LIC is greater than 15 mg Fe/g dw, consider increasing the dose to 14 mg/kg/day after 4 weeks.

During therapy:

- Monitor serum ferritin monthly. Interrupt treatment when serum ferritin is less than 300 mcg/L and obtain an LIC to determine whether the LIC has fallen to less than 3 mg Fe/g dw.
- Monitor LIC every 6 months.
- After 6 months of therapy, if the LIC remains greater than 7 mg Fe/g dw, increase the dose of deferasirox to a maximum of 14 mg/kg/day. Do not exceed a maximum of 14 mg/kg/day.
- If after 6 months of therapy, the LIC is 3 to 7 mg Fe/g dw, continue treatment with deferasirox at no more than 7 mg/kg/day.
- When the LIC is less than 3 mg Fe/g dw, interrupt treatment with deferasirox and continue to monitor the LIC.
- Monitor blood counts, hepatic function, and renal function [see *Warnings and Precautions (5.1, 5.2, 5.4)*].

Restart treatment when the LIC rises again to more than 5 mg Fe/g dw.

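### Inclusion 4 sets one entry dose for TDT and NTDT, twice the NTDT maximum in the appended labels, so NTDT patients at their labelled maximum cannot enroll

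*Protocol*

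**What the plan says.** Section 4 states that patients "must meet all of the following criteria to qualify for entry into the study", so the inclusion criteria are cumulative. Inclusion 3 in Section 4.1 admits both TDT and NTDT. Inclusion 4 requires more than three months of stable dosing and that the patient be "receiving the maximal dose (Jadenu: 28 mg/kg or Exjade: 40 mg/kg". The synopsis population statement repeats it: "receiving the maximal dose of oral commercial deferasirox (DFX), Jadenu: 28 mg/kg or Exjade: 40 mg/kg". Neither place gives a separate figure for NTDT.

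Section 3.2 supports the single figure with "The maximum recommended dosage of DFX as Jadenu is 28 mg per kg body weight orally, once daily", naming no indication, although it has just said that the Jadenu starting dose depends on the indication.

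For dosing in the trial, Section 5.4 says "Patients will receive Exjade or Jadenu at their previous stable dose". DST-0509 is matched milligram for milligram to Jadenu, or scaled by 28/40 from Exjade.

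The appended labels separate the two indications:

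- Transfusional iron overload: Appendix B, label section 2.1, says "Doses above 28 mg per kg are not recommended" of Jadenu. Appendix A, label section 2.1, sets the same kind of limit for Exjade at 40 mg/kg.
- NTDT: label section 2.2 says "Do not exceed a maximum of 14 mg/kg/day" for Jadenu (Appendix B) and "Do not exceed a maximum of 20 mg/kg/day" for Exjade (Appendix A).

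The conversion table in Appendix B, label section 2.3, shows both sets of maxima side by side.

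**The concern.** The criterion is meant to select patients who respond poorly although their dose can go no higher. For NTDT it uses the ceiling of the other indication. NTDT patients who have reached their own labelled ceiling, the natural candidates for the trial, are turned away. The only NTDT patients who pass are those already taking twice the cap.

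Two things are at stake.

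- **Information.** NTDT patients appear in the primary objective (Section 2.1), the secondary PK objective (Section 2.2), inclusion 3 and the possible TDT/NTDT analysis (Section 8.5.2). That analysis depends on recruitment, so a shortage of NTDT patients could be put down to slow accrual when the criterion caused it.
- **Safety of any NTDT patient who enters.** Such a patient stays above the cap on the comparator and takes DST-0509 at the matched dose. Section 1.2 reports higher bioavailability of DST-0509 than of Jadenu on a molar basis in healthy volunteers, so equal milligrams need not mean equal exposure. The NTDT trials described in Appendix A, label section 6.1, used 5, 10 or 20 mg/kg/day of Exjade; none is reported at 40. The adult NTDT creatinine rules in label section 2.5 are written only for 5, 10 or 20 mg/kg of Exjade and 3.5, 7 or 14 mg/kg of Jadenu.

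**Working it through.** **Inputs**

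| Product | Entry dose, inclusion 4 (mg/kg) | Label maximum, transfusional overload (label 2.1) | Label maximum, NTDT (label 2.2) |
|---|---|---|---|
| Jadenu | 28 | 28 | 14 |
| Exjade | 40 | 40 | 20 |

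**Entry dose divided by labelled maximum**

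- Transfusional overload: 28/28 = 1.0 and 40/40 = 1.0. The criterion matches the label.
- NTDT: 28/14 = 2.0 and 40/20 = 2.0. The criterion is exactly twice the cap for both products.

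**Eligibility under the rule as written**

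- NTDT patient on Jadenu 14 or Exjade 20 mg/kg/day, at the labelled maximum: fails inclusion 4 and is excluded.
- NTDT patient on Jadenu 28 or Exjade 40 mg/kg/day, at twice the cap: passes inclusion 4.

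**What a qualifying NTDT patient receives**

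- Comparator: previous dose, 28 (Jadenu) or 40 (Exjade) mg/kg, for 28 days.
- DST-0509: 28 mg/kg from Jadenu, or 40 × 28/40 = 28 mg/kg from Exjade, for 28 days.
- Total: 28 + 28 = 56 dosing days. Half continue the existing prescription; the other half are on the investigational product.

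**Does the conversion survive an indication-specific rule?** The protocol's factor is 28/40 = 0.70. For NTDT, 14/20 = 0.70. It is unchanged.

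**Effect on the sample-size statement (Section 8.1).** The stated probabilities reproduce with the exact binomial. At a 12% diarrhea rate and N = 30, P(at least 1) = 0.978 and P(at least 2) = 0.890, against 0.98 and 0.89 in the protocol.

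These figures stay the same under the corrected criterion only if 12% also applies to NTDT patients at half the dose. Appendix A, label section 6.1, gives 12% for Exjade in beta-thalassemia (Study 1) and 5% in the NTDT studies, though the tables do not count reactions in the same way. As an illustration, assume 15 of 30 patients have NTDT and a 5% rate:

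- P(0 events) = 0.88^15 × 0.95^15 = 0.068, so P(at least 1) = 0.93.
- P(1 event) = 0.068 × (15 × 0.12/0.88 + 15 × 0.05/0.95) = 0.193, so P(at least 2) = 0.74.

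With no NTDT patients the values remain 0.98 and 0.89. The true NTDT share is not planned, so the result lies somewhere along that range.

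**The case against.** The strongest reply is that the single dose may be intended. The synopsis rationale speaks of patients inadequately controlled on high doses. The protocol also departs from indication-specific label values elsewhere: it uses one ferritin threshold of 800 mcg/L, where the labels use 1000 for transfusional overload and 300 for NTDT. It says that inadequate response is defined from the literature. A restrictive criterion is not an error in itself. But nothing in the protocol states or justifies dosing NTDT patients above the cap, and Section 3.2 presents 28 mg/kg as though it were the maximum for everyone. Intent is possible but unsupported.

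Other points carry some weight:

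- **Limited consequence.** This is a pilot of up to 36 patients with no NTDT target, and the stratified analysis is conditional on recruitment. That bounds the importance, but Sections 2.1 and 2.2 still name NTDT.
- **Safety.** DST-0509 replaces 28 days of a prescription the patient already took stably, and the design includes three 7-day washouts. The change is therefore 28 days on a different, possibly more bioavailable, formulation, not extra days of treatment. This stands.
- **Transfused NTDT patients.** Someone classed as NTDT but heavily transfused might have been dosed under label section 2.1. The documents do not settle this.
- **Label version.** Section 15 cites labels dated 08/2016 (Exjade) and 10/22/2015 (Jadenu); those appended are revised 10/2013 and 3/2015. The caps used here are those of the appended versions.
- **Cost of the fix.** Half-dose NTDT patients could lower the chance of seeing diarrhea events, as the illustration shows. This is a reason to report by dose, not to leave the criterion alone.

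**Conclusion.** The concern holds. As written, inclusion 4 gives the wrong eligibility result for NTDT patients at their labelled maximum. It admits only those at 2.0 times the cap, for Jadenu and Exjade alike, who then have 56 dosing days at that level or its matched DST-0509 equivalent. The protocol offers neither an NTDT rule nor a justification.

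The TDT part of the trial is unaffected and the pooled analyses remain feasible. What is compromised is the trial's ability to say anything about NTDT, together with the dosing of any NTDT patient who enters. The number affected cannot be given, because no NTDT share is planned. The conclusion rests on the NTDT caps in the appended label versions. It should be corrected, but it does not invalidate the design.

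**What to change.** Restate inclusion 4 in Section 4.1, and the matching text in the synopsis (population and inclusion criteria), as the maximal dose for the patient's indication:

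- TDT: Jadenu 28 or Exjade 40 mg/kg/day.
- NTDT: Jadenu 14 or Exjade 20 mg/kg/day.

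DST-0509 is then matched to that dose: 28 mg/kg for TDT and 14 mg/kg for NTDT. The 28/40 conversion needs no change. Correct Section 3.2 to say that the maximum depends on the indication. As an editorial matter, align the closing paragraph of Section 1.2, which describes a TDT-only trial.

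The alternative is to remove NTDT from the objectives, population and analyses. That avoids a mixture of doses but gives up the NTDT question.

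The cost of the first option is amendment wording, plus reporting. Pooled data would hold two absolute DST-0509 dose levels, so exposure summaries should be shown by dose or dose-normalised, and adverse-event summaries should also be shown by dose. Section 8.1 should say that its probabilities assume the same diarrhea rate in both groups. The within-patient comparison stays dose-matched. Splitting by dose thins cells that are already small, because Section 8.5.4.2 does not pool Jadenu and Exjade.
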